11.0 Data Management

Paper consent will be stored in a locked cabinet in the PT department. All data management will be conducted using the REDCap platform developed and housed at MUSC. All other collected data will be stored electronically in the MUSC OCIO approved secure SharePoint system.

Access to this database will be restricted based on netID permissions to a secured server and will only be accessible to IRB study personnel. Identifying information will be removed from the primary database. Identifying information will be stored in a separate file with a unique identifier assigned to the patient to link the two datasets.

Our data and safety monitoring plan will be continuous, close monitoring by the study investigator/co-investigators of all participants. The PI and Co-I's will meet every 25 patients to discuss data and safety monitoring. During these meetings we will look for any negative trends

in the data we have collected (vitals, NIH stroke scale- i.e., stroke severity, and functional mobility scores) that could indicate adverse events and provide a timely summary report of adverse events to the IRB/NIH.

Any reportable safety events that are unexpected, serious or may be related to the subjects' participation in this research will be reported to the MUSC IRB in accordance with their policies.

Once the Principal Investigator (PI) determines that an adverse event meets the IRBs' reporting requirements, the PI will report the SAE, and related safety information, to the IRB. For reasons of confidentiality, subjects' names will not be included in the report. If the adverse event results in the need to revise the informed consent, or other study documents, the PI will submit a study amendment to the IRB. Any trend in a type of adverse event will be relayed to the IRB as soon as the trend is noted. All events that do not meet the criteria of significant or trending, will be recorded in a summary form and included at the close of the study. Per consistency with the NIH guidelines- all serious and significant adverse events involving risks to a participant or suspension/termination of IRB approval for this study will be immediately reported to the sponsor.

12.0 Outcomes and Analysis

Goal enrollment is 168 participants. Based on the past literature, in similar populations the standard deviation of PASS measurements is at the most 7.20.⁵ Using this, with a sample of 42 patients in each group, with 95% confidence at the end of the study we can estimate this difference within a margin of error of 2.8.

The primary outcome measure will be the change in postural assessment stroke scale scores from time of PT evaluation to hospital discharge. A factorial design will allow for a test of intensity (vs control) and duration (vs control) through pooling across treatment arms. Using the table below, margins (A+C, B+D, A+B, C+D) need to each be 104 given a mean difference of 2.8, standard deviation of 7.2, 80% power and 5% type I error. Given that this is an early phase study, we can increase the type I error to 10% which would decrease the overall sample size needed to 168 patients (42 per arm) whilst still maintaining 80% power.

	Low Intensity	High Intensity	Totals
Low Duration	A	B	A+B
High Duration	C	D	C+D
Totals	A+C	B+D	A+B+C+D

We are planning to conduct the analysis using intention to treat paradigm. In a preliminary analysis we will compute all summary statistics. Initial plots, such as spaghetti plots, will be used to guide our analyses. A general linear mixed model approach will be used to analyze all the outcomes. This model will account for the correlations between time points using either a compound symmetric or spatial structure for the covariance matrix. Post-hoc analyses using Tukey type adjustments will be performed to obtain least squares estimates of the differences between the two randomized groups. Although the study is powered based on only the primary

outcome (PASS), we will apply multiple comparisons adjustments for the rest of the outcomes, using Bonferroni corrections. We will test for the assumptions using diagnostic procedures and take appropriate actions if needed. Also, we will define an outcome to be ‘favorable’ or ‘unfavorable’ based on a threshold and apply generalized linear mixed models with logistic link and repeat the analyses. We will attempt to minimize drop-outs but in case of missing data, we will assume Missing at Random or Missing Completely at Random. If necessary, we will perform multiple imputations. For all analyses, we will use SAS, (MIXED, GLIMMIX, MI and MIANALYZE).

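### Section 12 states planned precision at 95% confidence but sizes the trial at a 10% type I error, and names no level for the final test or interval

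*Combined protocol and SAP*

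**What the plan says.** Levels of confidence or error for the primary outcome, the change in PASS from PT evaluation to discharge, appear only in Section 12.0 (Outcomes and Analysis).

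- **Precision.** With an SD of at most 7.20 and 42 patients per group, the plan says that "with 95% confidence at the end of the study we can estimate this difference" to within 2.8 points. It does not define which difference is meant.
- **First sizing step.** The pooled margins of the two-by-two table "need to each be 104 given a mean difference of 2.8, standard deviation of 7.2, 80% power and 5% type I error".
- **Adopted size.** "Given that this is an early phase study, we can increase the type I error to 10" percent, which brings the total to 168 (42 per arm) "whilst still maintaining 80% power".
- **Analysis paragraph.** It describes intention to treat, mixed models, Tukey-type and Bonferroni adjustments and multiple imputation. It gives no significance level, confidence level or sidedness for the primary tests.

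Allocation is 1:1:1:1 (Section 9.0), so each pooled margin holds 84 patients.

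**The concern.** The 95% statement corresponds to a two-sided 5% test, while the adopted sample size rests on 10%. Both are in the sample-size text, the 10% is worded only as something that can be done, and nothing later says which level governs the final analysis.

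The stated power depends on that choice. An analyst who takes up the 95% level, or simply the conventional 5%, would be working with less power than the plan claims. For a result with p between 0.05 and 0.10, the level could be settled after the data are seen, and prespecification is meant to remove that choice.

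**Working it through.** **Inputs (Section 12.0):** difference 2.8; SD 7.2; power 80%; type I error 5%, then 10%; 42 per arm, hence 84 per pooled margin. Sidedness is not stated and has to be inferred. Figures use the normal approximation unless marked as t.

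**Step 1. Reproduce the plan's sizes.** n per margin = 2 × [(z_α + 0.8416) × 7.2 / 2.8]².

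| Type I error | z_α | n per margin | Plan |
|---|---|---|---|
| two-sided 5% | 1.960 | 103.8 | 104 |
| two-sided 10% | 1.645 | 81.8 | 84 |
| one-sided 5% | 1.645 | 81.8 | – |
| one-sided 10% | 1.282 | 59.6 | – |

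Only two-sided 5% followed by two-sided 10% fits the pair 104 and 84 (the second to within 3%). The interval that matches the adopted design is therefore a 90% interval.

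**Step 2. Power at 84 versus 84.** SE = 7.2 × √(2/84) = 1.111, and 2.8 / 1.111 = 2.520.

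- Two-sided 10%: Φ(2.520 − 1.645) = 80.9% (80.7% by noncentral t on 164 df).
- Two-sided 5%: Φ(2.520 − 1.960) = 71.2% (70.7% by noncentral t).

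**Step 3. Where the two levels part.** The critical differences on 164 df are 1.838 at 10% and 2.194 at 5% (1.83 and 2.18 by normal approximation). An observed difference between them is significant at 10% while its 95% interval includes zero. For example, a difference of 2.0 has p = 0.072, a 95% interval of −0.18 to 4.18 and a 90% interval of 0.17 to 3.83.

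- If the true difference is 2.8, the chance of landing in this zone is 80.7% − 70.7% = 10.0% (9.7% by normal approximation).
- Under no effect, it is (10% − 5%) / 2 = 2.5% in the favourable direction, or 5% counting both directions.

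**Step 4. Planned precision.** Half-width = z × 7.2 × √(2/n).

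| Comparison | 90% | 95% |
|---|---|---|
| pooled, 84 vs 84 | 1.83 | 2.18 |
| arm vs arm, 42 vs 42 | 2.58 | 3.08 |

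None of these is 2.8. At 95%, a half-width of 2.8 needs 2 × (1.960 × 7.2 / 2.8)² = 50.8, about 51 per group. With 52 per arm (208 patients, the plan's 5% sizing) it is 2.77. The sentence may be a remnant of that larger design, but the document does not say so.

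**The case against.** A reader might infer that the plan contains two competing success rules, so that a p-value between 0.05 and 0.10 is positive by one and negative by the other. The document does not support that. The 95% sentence describes the precision that 42 per group would give. It sets no criterion and does not commit the report to a 95% interval. The only level tied to a test in the adopted design is 10%; the 5% step is openly replaced, with a reason given.

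Three further points stand:

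- The 95% sentence concerns 42 per group, whereas the 10% test concerns pooled margins of 84. Reading both as the same comparison is an inference. It is a plausible one, because the sentence follows the PASS SD and uses the same value of 2.8, but it is not stated.
- A 10% test beside a 95% interval is not in itself a contradiction, provided that the decision level is clear.
- The 71% arises only if the team departs from 10%. It is also the figure at an SD that the plan calls an upper bound; a smaller SD would raise power at either level.

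These points limit the concern but do not remove it. If neither sentence is a rule for the final analysis, the plan has no stated decision level for its primary outcome. Correcting the 2.8 alone would not supply one.

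**Conclusion.** The point holds as an unreconciled and unstated level, not as two conflicting decision rules. The claimed 80% power requires a two-sided 10% test; at two-sided 5% it is about 71% for 2.8 points. The choice of level would change the reading of an observed main effect between about 1.84 and 2.19 PASS points. That is about 1 trial in 10 for a given factor if the planned effect is true, and about 1 in 40 under no effect, counting favourable results only. The fault does not bias the estimate.

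These figures assume a two-sided test (inferred from the plan's sizes), SD 7.2, all 168 patients contributing, a simple two-sample comparison of pooled margins rather than the mixed model, and each factor tested without adjustment for the other. Any such adjustment would change them.

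**What to change.** In Section 12.0, choose one of the following and state it in the analysis paragraph:

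- Each primary main effect (intensity and frequency, the latter labelled duration in the Section 12.0 table) is tested two-sided at 10% and reported with its 90% confidence interval. Any 95% interval is labelled descriptive and is not the basis of the decision.
- Each primary main effect is tested two-sided at 5% and reported with its 95% interval, and the power for 2.8 points at 168 patients is restated as about 71%.

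In either case, say whether the level applies before or after any adjustment for testing two factors. Replace the precision sentence with the half-width for a named comparison at the chosen level: for the pooled main effects about 1.83 (90%) or 2.18 (95%), and for arm versus arm about 2.58 or 3.08.

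The cost is wording only, with no extra patients. Under the first option the relaxed level becomes visible in the reported interval; under the second the stated power falls.

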9.0 Study Design

This study will be designed as a randomized control trial with a 1:1:1:1 randomization. This study will utilize a stratified block randomization design and stratifying on the 4 NIHSS categories to randomly allocate a participate to a treatment group, while maintaining a balance across treatment groups. All patients will be identified and consented as soon as possible, ideally within 24 hours of admission to the stroke service. Patient's blood pressures will be obtained prior to PT treatment to ensure safety of mobilization. If systolic blood pressure is above 220mmHG, therapy services will not be performed at that time and therapist will follow up later in the day once patient is medicated for hypertension by nursing staff.

If a patient is randomized to the frequent physical therapy treatment group, they will receive PT services 2x/day for 3 out of the first 5 days of hospital admission and daily for the remainder of their hospitalization. Sessions will be 20-50 minutes in duration, based on patient tolerance. These PT sessions will include working on getting out of bed, transferring from bed to a chair, working on balance, strengthening the side of the body affected by the stroke, learning how to walk again and/or how to use a wheelchair if unable to walk.

If a patient is randomized to the intense physical therapy treatment group, they will receive PT services daily with treatment sessions being more difficult than a standard therapy session. During each PT session, the things that are difficult for the patient will be made even more difficult (by adding resistance or other challenges) in order to increase the intensity of the session. This is known as "Error Augmentation training" and will be implemented to target at least 3 post stroke deficits identified on evaluation.

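### The stated 95% margin of error of 2.8 does not follow from its own inputs: with SD 7.2 and 42 per arm it is about 3.1 for two arms and about 2.2 for a pooled main effect

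*Combined protocol and SAP*

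**What the plan says.** The first paragraph of section 12.0 (Outcomes and Analysis) is a precision statement. It says that "the standard deviation of PASS measurements is at the most 7.20", applies that value "with a sample of 42 patients in each group", and concludes that "with 95% confidence at the end of the study we can estimate this difference within a margin of error of 2.8". It does not define the difference it refers to.

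The second paragraph is a power calculation for the factorial comparisons. It first says that "margins (A+C, B+D, A+B, C+D) need to each be 104", taking 2.8 as the difference to detect, an SD of 7.2, power of 80% and a type I error of 5%. It then raises the type I error to 10% and arrives at 168 patients, 42 per arm, with power kept at 80%. The number 2.8 thus appears twice, once as a margin of error and once as the difference to detect.

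Section 9.0 (Study Design) describes a "randomized control trial with a 1:1:1:1 randomization", so 168 patients give four arms of 42 and factorial margins of 84. The analysis text in section 12.0 also plans Tukey-type adjustment for post-hoc group comparisons.

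**The concern.** The precision sentence supplies every input needed to check it: SD, group size and confidence level. A margin of error computed from them should reproduce, and this one does not.

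Arm-level precision matters here because some of the aims in section 1.0 compare single arms. Aim III sets increased intensity against increased frequency, and Aim IV sets the combination against intensity alone. A pooled main effect does not directly estimate the Aim III contrast, so for that question the relevant precision is that of 42 against 42. For the pooled comparisons on which the trial is powered, 84 against 84 is relevant. A reader who takes 2.8 at face value has the wrong precision for both: too optimistic for the arms, too pessimistic for the main effects.

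**Working it through.** **Inputs.** From section 12.0: SD 7.2, 42 per group, 95% confidence, stated margin 2.8; difference to detect 2.8, power 80%, type I error 5% and then 10%; 104 per margin at 5%. From section 9.0: equal allocation to four arms, hence 84 per factorial margin. Two-sided levels are assumed, because the plan does not state sidedness; two-sided 5% reproduces its 104.

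**The plan's power figures.** The number per margin is n = 2 × [(z for alpha + z for power) × SD / difference]².
- At 5%: 2 × [(1.960 + 0.842) × 7.2 / 2.8]² = 103.8, so 104 per margin. This matches the plan and means 52 per arm, 208 in total.
- At 10%: 2 × [(1.645 + 0.842) × 7.2 / 2.8]² = 81.8, so 82 per margin, against 84 planned.
- Power at 84 per margin and 10%: the standard error is 7.2 × √(2/84) = 1.111, and 2.8/1.111 − 1.645 = 0.875, which gives 80.9%.

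The power calculation therefore reproduces.

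**The precision figure.** The half-width for a difference of two means is quantile × SD × √(2/n).
- Two arms of 42: the standard error is 7.2 × √(2/42) = 1.571. At 95%, 1.960 × 1.571 = 3.08; with t on 82 df, 3.13; with t on 164 df (SD pooled over four arms), 3.10. At 90%, 1.645 × 1.571 = 2.58.
- Main effect, 84 against 84: at 95%, 1.960 × 1.111 = 2.18; at 90%, 1.645 × 1.111 = 1.83.

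**Other readings, 95%, SD 7.2.**

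| Quantity | Half-width |
|---|---|
| Mean of one arm of 42 | 2.18 |
| One arm against two pooled arms (42 vs 84) | 2.67 |
| One arm against the other three (42 vs 126) | 2.51 |
| Interaction contrast | 4.36 |
| Any two arms, Tukey over four arms (164 df) | 4.08 |

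The Tukey value is (3.671/√2) × 1.571 = 4.08. At 90% it is (3.266/√2) × 1.571 = 3.63. None of these figures rounds to 2.8.

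**What would give 2.8.** With two arms of 42, it needs an SD of 2.8 / (1.960 × √(2/42)) = 6.55, or a confidence level of about 92.5%. With SD 7.2 and 95%, it needs 2 × (1.960 × 7.2 / 2.8)² = 50.8 per arm; by the z formula, anything from about 49.0 to 52.7 per arm rounds to 2.8. At 52 per arm the half-width is 2.77 (z) or 2.80 (t, 102 df).

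**Size of the discrepancy.** 2.8/3.08 = 0.91 and 2.8/3.13 = 0.90, so the printed figure is 9% to 10% too narrow for two arms, about 0.3 PASS points. Against the main effect, 2.8/2.18 = 1.29, so it is about 29% too wide.

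**The case against.** The best defence is that 7.20 is described as an upper limit and applies to PASS measurements, whereas the primary outcome is a change score analysed in a mixed model. An effective SD near 6.55 would yield 2.8. That would follow from a change score with a baseline-to-discharge correlation near 0.59, or from baseline adjustment with a correlation of roughly 0.4. This limits the practical importance of the error but does not remove it: the sentence says it uses 7.20, and the plan gives no correlation.

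It can also be said that the sample size does not rest on this sentence, that the margin for the pooled tests is better than stated, and that 0.3 points is a small gap. All three are correct.

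A reader might infer more than the documents support:
- *That 2.8 was left over from the 52-per-arm version.* The match is close, but the plan gives no precision figure for that size, neighbouring sizes also round to 2.8, and 2.8 may simply repeat the difference to detect.
- *That 95% confidence contradicts a 10% test.* It does not. A plan may report 95% intervals and test at 10%.
- *That an observed arm difference of 2.8 would fail the plan's test.* Its unadjusted 95% interval, −0.3 to 5.9, includes zero. But at 90%, which matches the adopted type I error, the unadjusted interval is 2.8 ± 2.6, or 0.2 to 5.4, and excludes zero. The 95% interval is therefore not evidence of failure at the plan's own level.

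**Conclusion.** The precision statement is wrong on its own inputs. For two arms of 42 with SD 7.2, the unadjusted 95% margin is about 3.1; for a factorial main effect it is about 2.2. The figure 2.8 fits neither, nor any other standard contrast tried. The conclusion rests on the SD of 7.2 that the plan says it uses, equal arms of 42 with complete data, and two-sided intervals.

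The error is modest and confined to one sentence. It should not be read as a fault in the sample size: 168 patients at 10% type I error give 80.9% power for a main effect of 2.8. The resemblance to 52 per arm is a possible explanation, not a finding. The correction is still worth making, because the figure stands in the sample-size justification for the primary outcome and because the margin after the planned Tukey-type adjustment, about 4.1 at 95% if it covers all four arms, is further still from 2.8.

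**What to change.** Replace the precision sentence in section 12.0 with:

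*With SD 7.2 and 42 per arm, the unadjusted 95% margin of error is 3.1 points for a comparison of two arms and 2.2 points for a factorial main effect (84 vs 84); at 90% confidence these are 2.6 and 1.8. With Tukey adjustment over all four arms, the pairwise margin is about 4.1 (95%) or 3.6 (90%).*

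This defines the difference being estimated and separates unadjusted from adjusted precision. If the sponsor intended a smaller SD for the change score or for a baseline-adjusted analysis, the text should state that SD and the correlation behind it, and the margins should be recomputed.

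The cost is one sentence. The enrolment target, endpoint and tests stay as they are; the stated arm-level precision becomes slightly less favourable.

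### The primary model names neither evaluation PASS nor the NIHSS strata, and an SD described as that of PASS scores is used for a change, so power at 168 patients rests on an unstated correlation

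*Combined protocol and SAP*

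**What the plan says.** Section 12.0 defines the endpoint: "The primary outcome measure will be the change in postural assessment stroke scale scores from time of PT evaluation to hospital discharge". All outcomes are to be analysed with a general linear mixed model that allows for correlation between time points through a compound symmetric or spatial covariance. The section lists no fixed effects. It does not say whether the evaluation score is a response, a covariate or is subtracted.

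Section 9.0 describes 1:1:1:1 stratified block randomisation, "stratifying on the 4 NIHSS categories to randomly allocate a participate to a treatment group". Section 12.0 does not mention NIHSS.

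On variability, Section 12.0 says that "in similar populations the standard deviation of PASS measurements is at the most 7.20". The calculation for the pooled factorial comparison then uses this value directly, "given a mean difference of 2.8, standard deviation of 7.2, 80% power and 5% type I error", and arrives at 104 patients for every margin of the two-by-two table. On the grounds that the study is early phase, the plan continues: "we can increase the type I error to 10% which would decrease the overall sample size needed to 168 patients (42 per arm". The documents give no SD of change, no evaluation-to-discharge correlation and no dropout rate.

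**The concern.** There are two linked gaps.

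First, the model for the primary comparison is incomplete. Evaluation is one of the time points at which PASS is measured (Sections 5.0 and 9.0). If it is a response in a group-by-time model with free group means, then with complete data the evaluation-to-discharge contrast is the raw change-score comparison. The Phase I results in Section 3.0 are reported as group changes with an interaction p-value, which suggests a model of that kind. Baseline adjustment is never less precise than raw change, apart from a few degrees of freedom. Leaving out a prognostic stratification factor also tends to make standard errors too wide.

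Second, the SD of a score and the SD of a change are different quantities. If 7.2 belongs to a score, the stated 80% power holds for unadjusted change only at particular correlations.

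At stake are the stated power and the choice to work at 10% rather than 5%.

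**Working it through.** **Inputs from Section 12.0:** difference 2.8; SD 7.2; 80% power; error rate 5%, then 10%; 42 per arm, so 84 per pooled margin.

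**Assumptions:** two-sided tests (sidedness is not stated, but two-sided reproduces the plan's figures); equal SDs at evaluation and discharge; a within-arm correlation ρ of 0.3 to 0.8, which the documents do not give.

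**1. The plan's own figures.** n per margin = 2(z_alpha + z_power)² × 7.2²/2.8².
- 5%: 2 × (1.960 + 0.842)² × 6.612 = 103.8, so 104, as stated.
- 10%: 2 × (1.645 + 0.842)² × 6.612 = 81.8, so 82; the plan has 84.

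With 84 per margin, SE = 7.2 × √(2/84) = 1.111 and 2.8/1.111 = 2.520. Power is Φ(2.520 − 1.645) = 80.9% at 10% and Φ(2.520 − 1.960) = 71.2% at 5%.

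**2. If 7.2 is the SD of a score.** SD(change) = 7.2√(2(1 − ρ)), which equals 7.2 only at ρ = 0.5. SD(baseline-adjusted) = 7.2√(1 − ρ²), which never exceeds 7.2. Power = Φ(2.8/(SD × √(2/84)) − z).

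Example at ρ = 0.3 and 10%: the change SD is 8.52 and the SE 1.314, giving Φ(2.130 − 1.645) = 69%. The adjusted SD is 6.87 and the SE 1.060, giving Φ(2.642 − 1.645) = 84%.

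| ρ | SD change | Power at 10% | Power at 5% | SD adjusted | Power at 10% | Power at 5% |
|---|---|---|---|---|---|---|
| 0.3 | 8.52 | 69% | 57% | 6.87 | 84% | 75% |
| 0.4 | 7.89 | 74% | 63% | 6.60 | 87% | 79% |
| 0.5 | 7.20 | 81% | 71% | 6.24 | 90% | 83% |
| 0.6 | 6.44 | 88% | 80% | 5.76 | 93% | 88% |
| 0.7 | 5.58 | 95% | 90% | 5.14 | 97% | 94% |
| 0.8 | 4.55 | 99% | 98% | 4.32 | 99% | 99% |

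**3. If 7.2 is the SD of change.** Unadjusted power stays at 81% (10%) and 71% (5%). SD(adjusted) = 7.2√((1 + ρ)/2). Adjusted power at 5% is 88%, 85%, 83%, 80%, 78% and 76% for ρ = 0.3 to 0.8, so it now falls as ρ rises.

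**4. What 80% at 5% requires.** With 84 per margin, the residual SD must be at most 2.8/(2.8016 × 0.1543) = 6.48.
- Score SD, adjusted: ρ ≥ √(1 − (6.48/7.2)²), about 0.44.
- Score SD, unadjusted change: ρ ≥ 1 − (6.48/7.2)²/2, about 0.60.
- Change SD, adjusted: ρ ≤ 2 × (6.48/7.2)² − 1, about 0.62.

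**5. Dropout.** With an assumed 10% loss (75.6 per margin) and 7.2 as a score SD, adjusted power at 5% is about 76% at ρ = 0.44, 79% at 0.5, 85% at 0.6 and 92% at 0.7. At 10%, a residual SD of 7.2 gives 77%.

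**The case against.** The strongest reply is that the plan is silent, not wrong. A mixed model with evaluation PASS as a covariate, or with a common baseline mean, would satisfy Section 12.0 as written and would already be adjusted. This stands. The point is an under-specified primary model, and the documents do not show that an unadjusted analysis was chosen.

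Four stronger readings are tempting, and the documents do not support them.

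- **The 10% error rate is probably unnecessary.** This needs a correlation that the documents do not give, and the condition reverses if 7.2 is really an SD of change. The stated reason for 10% is the early phase of the study.
- **Using a score SD for a change loses power.** The direction depends on ρ. Above 0.5 the SD of change is below 7.2, and from about 0.6 unadjusted change already reaches 80% at 5%.
- **Baseline adjustment guarantees 80%.** At 10% it does so only if 7.2 is a true ceiling for the score SD and all 168 are analysed. With an assumed 10% loss, adjusted power is 77% at ρ = 0.
- **Omitting the strata has a known cost.** The documents do not say how much outcome variance NIHSS explains. A severity effect common to both visits cancels from a change, and the gain beyond evaluation PASS may be small. Where there is a cost, it is a conservative test, not extra false positives.

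**Conclusion.** The point holds as a gap in specification with a material but uncertain effect on power. Section 12.0 should name the terms of its primary model, and its SD does not match its endpoint as described.

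If 7.2 is a score SD and ρ is 0.3 to 0.4, unadjusted change gives 69% to 74% power at two-sided 10%, short of the stated 80%; baseline adjustment gives 84% to 87%. At ρ = 0.5 the figures are 81% and 90%. Adjustment is at least as good throughout, apart from the degrees of freedom.

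Whether 5% is attainable with 168 patients turns on a residual SD of at most about 6.48 with everyone analysed, and the documents cannot settle that. The gain from the strata cannot be quantified from them either.

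All figures concern the pooled main effects (84 v 84). Comparisons of single arms, as in Aims I to IV, have 42 v 42 and at SD 7.2 only 55% power at 10% and 43% at 5%.

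**What to change.** - Specify the primary model: discharge PASS (or change) with evaluation PASS and NIHSS stratum as covariates, or a longitudinal model with a common baseline mean across arms plus NIHSS stratum.
- State whether 7.2 is the SD of a score or of a change, and state the sidedness of the test.
- Show power for assumed correlations of 0.3 to 0.8, with an explicit allowance for dropout. Section 14.0 provides for withdrawal on worsening status or ICU transfer, and N is not inflated for it.
- Estimate the correlation and the SD of change in advance. Phase I measured PASS at admission and discharge, so its data are the natural source. Then fix 5% or 10% once. Do not tie the error rate to a correlation observed during the trial: the requirement concerns the residual SD and the number analysed, and a correlation alone does not determine either.

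The cost is SAP wording and one reanalysis of existing data. Evaluation PASS and NIHSS are already collected, and the covariates use about 4 degrees of freedom (1 for evaluation PASS, 3 for four strata).
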